#### Research Objective

The primary objective of this investigation is to identify utility of Ketamine as a clinically effective and efficient adjunctive treatment modality for the acutely suicidal patient in the ED setting. Secondary objective is to investigate prospectively if the anti-suicidal effects are able to have lasting effect up to one week within the vulnerable period post discharge.

#### Detail How Many Groups or Arms are in the Study and what each Receives

This study is designed as an RCT with two arms, Experimental vs. Placebo. Table 1 shows a detailed description of both arms. This will be a triple masked study. The patient, healthcare providers, and outcomes assessor will be blinded.

**Table 1:** Description of Experimental Arms

| Arm                              | Intervention/Treatment  |
|----------------------------------|---|
| Experimental:
Ketamine | Drug: Ketamine (Ketalar)
Single dose IV ketamine, 0.5 mg/kg in 100 cc Normal Saline, infused over 40 minutes
Other Name: N-methyl-D-aspartate (NMDA) glutamate receptor antagonist |
| Placebo: Saline           | Drug: Normal Saline (NS)
100 cc infused over 40 minutes   |

## Randomization Procedures

Randomization will be done through permuted block randomization and stratified for history of mood disorder (e.g., major depression, bipolar disorder, dysthymia). Due to the small size of this study, block randomization will ensure an equal number of treatment and controls. Randomization can lead to unbalanced groups with respect to prognostic factor. Because 60% of those who commit suicide have a mood disorder, this study will be stratified by this prognostic factor. This computer-generated list, will provide a subject identifier. This list of subject identifier and procedure status will serve secondarily as an audit trail

## Methods and Materials

All procedures in the management of the acutely suicidal patient will be in accordance with the standard of care, which includes a focused history and physical by an Emergency Medicine physician. Figure 1 demonstrates the flow of investigational procedures. The EM provider shall medically screen the patient and include appropriate ancillary studies. For example, if a patient is altered, intoxicated, sick-appearing, or exhibiting a clinical toxicodrome, standard labs, EKG, or imaging will be ordered per standard of care. All female patients will have a urine HCG documented. Then, screening for admission to the psychiatric department will be done by the mental health liaison. This standard procedure will serve secondarily as the pre-screening method for this investigation. This will minimize duplication of work.

Once the patient is deemed "to be admitted to the psychiatric unit," the physician will check the Electronic Medical Records (EMR) for inclusion and exclusion criteria. If a patient's current medication has a possible interaction with ketamine, the ordering provider will consider consulting with the inpatient pharmacist about possible contraindications, which will be documented in the chart. Once screened as a potential subject for the study, the patient will be approached for consent. Consent explaining the research protocols, benefits, and risks will be obtained once by a member of the investigative team. Consent will be obtained from a clinically sober intervention-eligible patient, who is accepted to inpatient psychiatry. It will be obtained while in the ED. Subjects will consent on an individual basis. Consent will be documented on a standardized consent form approved by the IRB. Any female patient will undergo a pregnancy test to verify eligibility.

Once the patient is enrolled, the physician will calculate the dosage based on actual weight and place the order in the electronic medical record. The emergency department nurse assigned to the care of the patient will fax the order to the pharmacy. At this point, the pharmacy will follow the randomization instruction and schedule, and undergo three safety checks per pharmacy protocol. (Appendix D: Randomization List & Instructions.) The medication will be treated as a controlled substance and will require a nurse or clinician to pick it up from the inpatient pharmacy.

To attain a psychometric baseline, the patient will complete the BSSI and MADRS, on paper forms. After completion of baseline, the clinician will administer a single dose of IV ketamine, per experimental protocol procedure. The specific dose and route of administration were selected based on average dosage and administration from meta-analysis studies. A bolus of ketamine was another common route of administration. However, there is no statistical significance between this and the one selected. This study will not require any wash out periods or concomitant dosing regimens. This dosage and infusion regimen is not considered sedation.

During ketamine infusion, vitals will be checked q5min with serial pulse and blood pressure measurements, and patient will have continuous pulse oximetry (Pox), with all vitals connected to monitors at the nurse's and doctor's stations. In addition, an attendant will be present at all times as per suicidal patient protocol. Treatment will be stopped if pulse or systolic blood pressure increases > 25% of baseline, respiratory rate is sustained at < 7, Pox decreases below 92%, or if severe psychomimetic effects or agitation present.

If treatment is stopped before completion for any reason, the patient will be dropped from the study, and their symptoms will be treated as per usual protocol of the physician. For instance, for severe psychomimetic effects and agitation, benzodiazepines such as midazolam could be considered. If a negative side effect occurs and treatment is stopped, it will be reported to the research monitor immediately.

Post assessment psychometric testing will be repeated at three time points for both arms. The first time point will be 4 hours post treatment, which is the standard time to evaluate acute response to ketamine. This may be collected in the ED or in the Psychiatric Unit. Subsequent questionnaires will be completed either in the ED or in the Psychiatric Unit. ED nurses giving report to the Psychiatric Unit will indicate that the patient is enrolled in the study, and give the time of administration of the study intervention and will indicate when the next questionnaire should be completed. Based on the literature, 24 hours post treatment, our second time point is when half of patients treated with a single dose of IV ketamine have shown reduction in SI.

Finally, patients will perform psychometric tests, ideally, one-week post infusion. They will be called at their phone number on file. The follow up BSSI will be administered by a study evaluator. Forms will be filled out, placed in trial mailbox, data transferred onto spreadsheet.

*Potential difficulties:*

1. Continuation/Concomitant use of psychotropics influence the same neurotransmitter as ketamine, making it difficult to discern direct effects of ketamine.
2. Heterogeneity of patients, enhances generality, but reduces confidence in any conclusions drawn.
3. Difficulty lie inherently in treating those with mood instability and difficult-to-treat patients.
  - a.) Those with mood disorders (BD & MDD) may metabolize ketamine differently

*Potential limitations*

1. Sample size
2. Need for replication
3. Placebo effect
4. Enrollment is only available when eligible study personnel are present
5. Depression is a placebo-responsive illness. Because suicide risk varies with the nature of depressive or mood disorder, the placebo effect is uncertain. Increased placebo effect increases variance and poor signal detection.
6. Lack of translational studies, especially in neurobiology of suicide.
7. SI measures suicide risk. However, it does not measure other psychological constructs associated with increased suicidal risk, such as hopelessness.
8. Lack of variety of outcome measure limits the study.
9. There is no established clinical biomarker predictor of ketamine.

[figure not shown]

Figure 1: Flow of Experimental procedure

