### Duties

The research monitor will perform **oversight** functions. This will encompass the following duties:

1. Observation of recruitment, enrollment, and consenting.
2. Monitor the study intervention and interaction between investigators and subjects.

3. Examine monitoring plans and reports and review data matching, collection, and data analysis procedures.

*Authorities*

In the event a problem is identified, the monitor will have the authority to stop a research protocol, remove individual subjects from a study, and take whatever steps are necessary to protect the safety and well-being of subjects until the IRB can assess the monitor's report.

The monitor is required to promptly report her medical monitoring and oversight monitoring observations and findings to the IRB or other designated official

If applicable, you may nominate an individual to serve as the Research Monitor:

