## Experimental Procedure

1. Baseline evaluation of suicidal severity (BSSI) & degree of depressive symptoms (MADRS-S) will be evaluated through self-administered questionnaires.
2. The experimental and placebo arms will receive a single dose of IV ketamine, 0.5 mg/kg in 100 cc NS or 100 cc of NS infused over 40 minutes.
3. Post ketamine re-evaluation of outcome measures at four and twenty-four hours will determine clinical effectiveness of ketamine intervention
4. Inspection of admission and transfer time provides time measurement for LOS. This secondary measure is needed to determine efficiency of intervention.
5. Post ketamine re-evaluation of outcome measure at one-week post infusion will elucidate ketamine's durability of effect.

**Table 2:** Description of activities at time points during the study

|  | Study Visit 1
Baseline ( $t_0$ ) | Study Visit 1
4 hours ( $t_1$ ) | Study Visit 1
24 hours ( $t_2$ ) | Study Visit 2
1 week ( $t_3$ ) |
|--|-------------------------------------|------------------------------------|-------------------------------------|-----------------------------------|
|  |                                     |                                    |                                     |                                   |

|  |   |   |   |   |
|--|---|---|---|---|
| Eligibility review and confirmation                    | X |   |   |   |
| Education regarding research & Informed Consent signed | X |   |   |   |
| History & Physical                                     | X |   |   |   |
| Randomization  | X |   |   |   |
| Dispense study drug                                    | X |   |   |   |
| IV Ketamine  | X |   |   |   |
| Vital Signs & ADR* monitored                           | X | X | X |   |
| Review adverse events                                  | X | X | X |   |
| Psychometric testing                                   | X | X | X | X |

\*ADR: Adverse drug reaction

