### **13.6 Withdrawal from Study Participation:**

Explain the process for withdrawal and specify whether or not the subjects will be given the opportunity to withdraw their data or specimens in the event they wish to withdraw from the study

Per Informed Consent Form:

"If you choose to participate, you are free to ask questions or withdraw from the project at any time without prejudice to your future care. Any new significant findings developed during the course of the research, which may affect your willingness to participate further, will be explained to you. Please notify [name] at [contact], [name] at [[contact]](mailto:[contact]) or [name] at [contact] to ensure an orderly termination process.

If you withdraw, you will no longer receive study drugs or treatments that are part of the study, unless these are also part of your normal drugs or treatments. Your withdrawal will involve no loss of benefits to which you are otherwise entitled. If you withdraw from this study, your data will be included in the data analysis for this project."

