## (2) Justification of Risks

Ketamine holds a high degree of safety. In a review that describes over 70,000 patients only a single cardiorespiratory event of lasting significance was reported. Fully dissociative patients maintain their pharyngeal reflexes.

| Risk   | Justification & Mitigation  |
|--|---|
| 
Transient Psychedelic effects are disturbances in visual and auditory perception, mood, body image, and time. Patient may experience feelings of floating, conscious dreams, or hallucinations. These effects occur between 50 and 200 ng/ml with more severe effects at higher doses.
 | 
Dissociative symptoms are transient and will peak at 40 minutes and resolve within 120 minutes.
 
To mitigate psychiatric discomfort, pre-induction coaching will be provided. This is where the patient will be informed that they may have vivid dreams.
                       |
| 
Hemodynamic changes are extremely rare with ketamine use, especially with such a slow infusion.
  | 
Signs of psychiatric discomfort will be managed with titratable sedatives (eg, midazolam) on an as needed basis.
 
Will be monitored hourly. Mild increases in heart rate can be mitigated by sympatholytic agents.
   |
| 
Psychotomimetic effects
   | 
Treatment will be stopped if pulse or systolic blood pressure increases > 25% of baseline, respiratory rate is sustained at < 7, or if severe psychomimetic effects or agitation present.
 
Can be mitigated through slow infusion or concomitant use of benzodiazepines if needed clinically.
 |
| 
Narcosis (absence of verbal response) at 0.5 mg/kg. This phenomenon is more likely with a quicker infusion.
   | 
This will be lessened or negated by mixing the dosage of medication in 100cc of NS and infusing slowly over 40 minutes.
  |
| 
Hypersalivation. Less likely at this concentration and with slow infusion.
   | 
This side effect can be addressed with concomitant use of glycopyrrolate if clinically indicated.
   |
| 
Nausea and vomiting. Less likely at this concentration and with slow infusion. Generally, occur after emergence from dissociative state.
  | 
This side effect can be addressed with use of ondansetron if clinically indicated.
  |

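### A patient whose infusion is stopped early is dropped from the study, and no visible text keeps that patient in the scheduled 4 h and 24 h safety reviews

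*Combined protocol and SAP*

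**What the plan says.** Section 10.1, Methods and Materials, sets the stopping criteria: "Treatment will be stopped if pulse or systolic blood pressure increases > 25% of baseline", a sustained respiratory rate below 7, oximetry below 92%, or severe psychotomimetic effects or agitation. The consequence of a stop follows in the next paragraph: "If treatment is stopped before completion for any reason, the patient will be dropped from the study". Symptoms are then handled as the physician usually would, with midazolam named as an example. One notification is attached: "If a negative side effect occurs and treatment is stopped, it will be reported to the research monitor immediately".

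Table 2 (section 10.1, Experimental Procedure) has two safety rows, one for vital signs and ADR monitoring and one labelled "Review adverse events". Both are marked at baseline, 4 h and 24 h. The table has no line for a patient whose infusion was stopped.

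Section 13.6 covers a patient who chooses to leave: "If you withdraw, you will no longer receive study drugs or treatments that are part of the study". It keeps that patient's data in the analysis. It does not say whether safety review continues.

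**The concern.** The listed reasons for stopping are all safety signals, so the rule falls mainly on patients who have just had a reaction. Stops for other reasons are caught too. If such a patient leaves the study, the two scheduled occasions for recording what happened next go with them.

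At stake are later events, chiefly non-serious ones, and a record of when the reaction resolved. Section 14.1 says: "Dissociative symptoms are transient and will peak at 40 minutes and resolve within 120 minutes". The 4 h review is the first Table 2 occasion after that point, so it is the natural place to document that recovery happened as expected. Section 14.1 also notes that respiratory depression or apnea, though extremely rare, may occur with concomitant midazolam, and midazolam is the rescue drug suggested for some stopped patients.

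This point concerns safety follow-up only. How stopped patients are handled in the efficacy analysis is a separate question.

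**Working it through.** The plan gives no figure on this point to reproduce. The check is mainly a comparison of texts, followed by a small count.

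**1. Does the rule cover both arms?** Yes. It names no arm, both arms receive a 40-minute infusion, and treating staff are blinded. The monitoring paragraph before it speaks of the ketamine infusion, but the drop rule is not so limited.

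**2. Does any visible text keep a stopped patient in the 4 h and 24 h reviews?**

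- *Report to the research monitor (10.1).* It covers the side effect that stopped treatment. It schedules nothing afterwards.
- *Monitor's authority (5.2, Duties).* The monitor may "take whatever steps are necessary to protect the safety and well-being of subjects". This is discretionary.
- *Reporting to the IRB (16.1).* Serious events in enrolled subjects are reported within 24 h of being discovered. Non-serious events go by the same route only if unexpected and possibly related. Psychotomimetic effects, hemodynamic changes, nausea and anxiety are already listed as risks in 14.1, so non-serious cases would ordinarily not count as unexpected. Their visible route is the annual summary, which can hold only what someone recorded.
- *Handover (10.1).* The ED nurse tells the Psychiatric Unit that the patient is enrolled, when the study treatment was given and when the next questionnaire is due. No handover is described for a dropped patient.
- *Withdrawal (13.6).* It covers the patient's own choice and is silent on safety review.
- *Clinical care.* Both arms are admitted. The ketamine intoxication overview in 16.1 ties the disposition of uncomplicated cases to symptom resolution. This is care, not study recording.

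None of these restores the two scheduled occasions.

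**3. Count per stopped patient.** The two Table 2 safety rows share the same times, so they form two review occasions after the infusion: 4 h and 24 h.

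- *Dropped* ends study activities: 2 of 2 occasions lapse.
- *Dropped* means removal from the efficacy analysis only: 0 of 2 lapse.

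Timing: 4 h = 240 min, against expected resolution of dissociative symptoms within 120 min.

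**4. Illustration only.** The documents give no stopping rate. Assume a rate *s* among the 31 ketamine patients (section 11.4), with independent stops and the plain reading. Expected stops = 31 × *s*. Occasions lost = 2 × 31 × *s*, out of 2 × 31 = 62 scheduled in that arm. Chance of at least one stop = 1 − (1 − *s*)^31.

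| Assumed *s* | Expected stops | Occasions lost (of 62) | Chance of at least one |
|---|---|---|---|
| 5% | 1.55 | 3.1 | 80% |
| 10% | 3.1 | 6.2 | 96% |
| 20% | 6.2 | 12.4 | 99.9% |
| 30% | 9.3 | 18.6 | over 99.9% |

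The table shows only that, even at a 5% rate, the situation would probably arise at least once. It does not estimate the loss in this trial.

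**The case against.** The strongest reply is that the plan never says the reviews end. *Dropped* may be loose wording for removal from the analysis. Section 11.1 speaks of excluding patients from the study in just that sense when too few scale items are completed. Section 13.6, the only visible text on what leaving means, ends treatment and keeps the data. The natural homes for a follow-up rule after a stop are the DSMP or DSMB plan (section 15.1), Figure 1, Appendix D and the consent pages, none of which can be seen. The patients are inpatients, so later events would probably be noticed.

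Much of this stands. It limits the point to the plain reading of the visible text and to scheduled recording. It does not remove the point, because the sentence in 10.1 is an instruction for conduct at the bedside, where a reader would most likely take it literally.

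A reader might infer more than the documents support:

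- *That stopped patients go unobserved.* Inpatient care, the monitor report and the monitor's powers all remain.
- *That serious events would go unreported.* Section 10.1 places enrolment before the dose is calculated and the infusion given. Section 16.1 covers enrolled subjects and makes no exception for stopped infusions.
- *That dissociative symptoms are unmonitored because the hourly checks concern only hemodynamics.* The words "Will be monitored hourly" stand in a section 14.1 table whose row boundaries have shifted in the extracted text, so no firm contrast can be drawn.

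**Conclusion.** The point holds in a limited form and is worth correcting. As written, the rule takes a patient whose infusion is stopped, in either arm, out of the study, and no visible text keeps that patient in the 4 h and 24 h safety reviews. The size is two review occasions per stopped patient on the plain reading and none on the efficacy-only reading. No total loss or size of bias can be given without a stopping rate and a later-event rate.

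The likely loss is scheduled recording of later non-serious events and of resolution. The conclusion assumes that *dropped* carries its ordinary operational meaning and that the unseen material does not already provide for these patients. Confidence is moderate for that reason.

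**What to change.** Leave the efficacy handling to a separate decision and add to section 10.1, Methods and Materials, after the rule on stopped treatment:

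> A patient whose infusion is stopped early still has the Table 2 vital-sign/ADR and adverse-event reviews at 4 h and 24 h after the infusion ends, unless consent is withdrawn; the handover to the Psychiatric Unit gives the start and stop times and any rescue drug.

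An optional clarification in section 16.1 is that enrolled subjects include those whose infusion was stopped. The enrolment sequence already implies this.

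The cost is small, because the reviews and the handover already exist and the patients are being admitted. The downsides are slightly more data collection and recorded event rates that may look less favourable. Adding a sentence, rather than deleting the drop rule, leaves psychometric follow-up and the efficacy population unchanged. If the unseen material already provides these reviews, a cross-reference to it would be enough.

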The BSSI will measure the severity of SI. It is based on the interviewer rated version of the original Scale for Suicidal Ideation (SSI), which is one of the few document suicide assessment tools with predictive validity for suicide completion.42 The internal reliability, test and retest validity, as well as invariance over time has been demonstrated for the BSS. 43, 45 Furthermore, the first five items of the BSSI are a common clinical screening for the presence of suicidal thoughts.40 For these reasons, the BSSI was chosen as our primary outcomes measure. Two studies have indicated that the cut off between high and low risk is a BSS  $\geq 2$ .43, 45 A recent investigation has determined BSSI  $\geq 6$  is predictive of future suicide attempts. 53 These two values will serve in our analysis.

The Montgomery- Åsberg Depression Rating Scale (MADRS) is a widely known 10 item clinician administered measure of depression severity.46 Since its development in the late 1970s, it has become more popular than the gold standard, Hamilton rating scale for Depression (HAM-D). It is considered to be more sensitive to change, just as effective, and simpler to use clinically.47 However, the reliability depends on good interrater agreement.48 Difficulties in clinical trial to show signal detection for known effective drugs have implicated clinician administered measurement as a possible source of error. To avoid poor interrater reliability, rater bias, and variable interview quality,48 this trial will utilize the self-administered version of the MADRS-S.49 This has 9 items and

a total score ranging from 0 to 27.50 The scoring of MADRS-S has shown to be similar to that of physician scoring.

The emotional pain of the suicidal patient requires empathetic care that may not always be possible with the time pressures, volume, and pragmatic nature of the ED environment. A pharmacologic intervention with rapid effects to decrease SI would play a vital role in improving the standard of care for this vulnerable population.

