#### Secondary outcomes:

**Specific aim 2:** Determine if this protocol for ketamine holds its effectiveness over time post infusion.

**Hypothesis 2:** The effects of ketamine can last up to a week post infusion.

Primary outcome measures of SI will be through self-administered Beck Scale for Suicidal Ideation (BSS or BSSI or SSI). The self-administered version of Montgomery- Åsberg Depression Rating Scale (MADRS) will be used to measures degree of concomitant depression symptoms. These patient-level data will serve as baseline comparatives. Subjects shall be randomized by the pharmacy and designated to either ketamine treated or saline placebo arm, with both the treating nurse and physician blinded. The experimental arm shall receive 0.5 mg/kg IV ketamine infusion over 40 minutes. To test for effectiveness within groups, we will measure outcomes at two different time points, 4 and 24 hours post infusion. To evaluate effectiveness between groups we will compare results between treatment and placebo arms. To test for specific aim 2, and to maximize response rate, a phone call will be made, one week after the initial questionnaire was done.

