Suicidal patients, subjectively identified by clinician, upon admission to the ED will be medically cleared by the EM physician, and then meet with the mental health liaison to be screened for admission to the psychiatric department, per normal standard of care. Study investigators will not be available around the clock, but when available will begin the pre-screening method for this investigation. The treating physician will pre-screen them for inclusion and exclusion criteria per an IRB approved check list (Appendix D: Criteria Checklist).

The patient will be approached for informed consent in accordance to with 21 CFR 50. They will be provided with a written document that embodies the elements of the informed consent. The consent will be presented orally to the subject with a witness. Once presented the subject will be given a reasonable time to review the contents and inquire information. Upon signing of the form, a copy shall be given to them.

Once consent is obtained, they will be presented with a paper form to complete the BSSI and MADRS-S. These measures will serve as baseline severity of suicidal wishes and plans, and degree of depression symptoms. Questionnaires will be stored in locked drawer's in the locked office the Division Officers in the Emergency Department, the Inpatient Mental Health ward, or the study coordinator.

Once the patient is deemed medically cleared by the treating physician, the study treatment will be ordered by an ED provider, per the randomization schedule, and administered by an ED nurse (Please see below for more detailed methodology). Those in the experimental arm will be treated with 0.5 mg/kg IV infusion of ketamine over 40 minutes. Those in the control arm will be treated with 100 cc Saline infusion over 40 minutes. (Table 1) Since there are no pharmaceutical treatment specific for acute suicide, it is in accordance to the Declaration of Helsinki (DOH) to utilize a saline placebo control. Vitals will be checked every 5 minutes during infusion. Questionnaires will be repeated at four time points for both arms, once in the ED before drug administration, one at 4 (+/-1) hours post-infusion, whether in the ED or the psychiatric unit, another 24-36 hours after the infusion in the inpatient psychiatric unit, and lastly one-week (+1 day) post treatment by phone call.

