### Research Material to Be Collected

1. The protocol requires patients to submit the following data:
  1. Phone number and email
  2. To measure SI severity, Self-administered BSSI (Appendix D: Sample BSSI)
  3. Level of depression shall be measured by the self-administered version of Montgomery-Åsberg Depression scale (MADRS-S). (Appendix D: MADRS-S)
2. The following information are obtained per standard of care, and will be collected through chart review:
  1. Medical history
    1. Psychiatric history
    2. Current and or Previous Diagnoses
    3. Current/recent antidepressant medication
    4. Current psychotropic medications
  2. Time stamps (admission & transfer)
3. The following additional information will be collected
  1. Class: military or civilian
  2. Number of previous suicide attempts
  3. History of self-harm
  4. Recent use of antidepressants
  5. Any applicable ancillary studies such as labs or imaging modalities
  6. Appendix D: Sample Data Collection Sheet
4. Identifier will be maintained in a spreadsheet that correlates subject identifier number and subject name. This will exist in privileged shared folder that only Investigators have permission to access. Data sheets will be coded such that only subject identifier numbers will exist on them.
5. Waiver of Authorization for the Use of PHI will not be necessary because request for access of medical history for research purposes is a component of the consent document. A separate authorization for the use of email in the one week follow up will also be requested at the time of consent.

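### The BSSI changes from patient-completed paper to evaluator-administered phone call at one week, so within-patient change to that visit cannot by itself show durability

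*Combined protocol and SAP*

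**What the plan says.** Section 9.3 (Secondary outcomes) sets the mode of the main measure without any exception for a visit: "Primary outcome measures of SI will be through self-administered Beck Scale for Suicidal Ideation". Section 10.1 (Methods and Materials) gives the baseline procedure: "To attain a psychometric baseline, the patient will complete the BSSI and MADRS, on paper forms". For the 4-hour and 24-hour assessments the same section says only that questionnaires are completed in the ED or the psychiatric unit. Section 10.2 (Data Collection Tools) lists the BSSI only as a paper form, so paper at those two visits is an inference, though a natural one.

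The one-week visit is different. The schedule under General Approach places it "lastly one-week (+1 day) post treatment by phone call". Methods and Materials says of the patients that "They will be called at their phone number on file", and then that "The follow up BSSI will be administered by a study evaluator". The mode of the one-week MADRS-S is not stated.

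The one-week score is the evidence for Specific Aim 2 and Hypothesis 2. Item 5 of the Experimental Procedure says that "Post ketamine re-evaluation of outcome measure at one-week post infusion will elucidate" how durable the effect is, without saying which comparison decides it. In Table 6 (Section 11.6) the rows on BSSI across time points use a mixed model or repeated-measures ANOVA with group as the fixed factor, and their relationship column covers both within and between. No row has a term for mode, and the list of limitations in Section 10.1 does not mention the change.

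**The concern.** Who administers the scale and through which channel both change at one visit, for every patient, and that visit carries the durability claim. A patient may disclose more or less suicidal ideation to a person on the phone than on a form. If less, scores fall at one week for a reason unrelated to treatment, and a within-patient reading shows improvement held or extended. If more, a lasting improvement is hidden. Because no patient has a paper score at one week or a phone score earlier, no analysis after the event can separate the two. What is at stake is the conclusion on Hypothesis 2, if it is drawn from change within the ketamine arm instead of from the comparison with placebo.

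**Working it through.** **1. Mode by visit**

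| Visit | Who completes or administers | Channel | Source |
|---|---|---|---|
| Baseline | patient | paper | Section 10.1, Methods and Materials; Experimental Procedure item 1 |
| 4 h, 24 h | patient (inferred) | paper (inferred) | Sections 9.3, 10.1 and 10.2 |
| One week | study evaluator | phone | Section 10.1, General Approach and Methods and Materials |

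**2. Which contrasts carry the mode shift**

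Let θ be the true mean BSSI at one week, μ the true mean at 24 h, and m the mean shift caused by phone administration, with subscripts K and P for ketamine and placebo.

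- Change within the ketamine arm: (θ_K + m_K) − μ_K = true change + m_K. The shift enters in full. A time effect pooled over arms likewise contains the average shift.
- Arm difference at one week: (θ_K + m_K) − (θ_P + m_P) = true difference + (m_K − m_P). If m_K = m_P, the shift cancels.
- Group-by-time contrast: also true contrast + (m_K − m_P), with the same cancellation.

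**3. The plan's own figure, and the number of completers**

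Table 4 (Section 11.5) gives 25.5 per arm for a two-sample t-test at d = 0.8, alpha 0.05 and power 0.80. A two-sided noncentral-t calculation gives 25.52, so the figure reproduces. The plan enrols 31 per arm and assumes 10% dropout: 31 × 0.9 = 27.9, taken as 28. Nothing in this point depends on the sample size being right.

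**4. Illustration for a within-arm test**

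The documents give neither a mode effect nor a within-patient correlation, so both are assumed. Suppose no true change from 24 h to one week, equal SDs at the two visits, and a pure additive shift of s SD. The SD of the change is √(2(1 − ρ)): 1.0 at ρ = 0.5 and 0.775 at ρ = 0.7. The paired t statistic has noncentrality s√28 / √(2(1 − ρ)) on 27 degrees of freedom. For s = 0.3 and ρ = 0.5 that is 0.3 × 5.29 / 1.0 = 1.59.

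Probability of a significant result at two-sided 0.05:

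| Assumed shift (SD) | ρ = 0.5 | ρ = 0.7 |
|---|---|---|
| 0.1 | 8% | 10% |
| 0.2 | 18% | 26% |
| 0.3 | 33% | 51% |
| 0.5 | 72% | 91% |

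Table 6 does not list this paired test. The figures show how sensitive a within-arm reading is; they are not error rates of the planned analysis.

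**5. Check of the randomised contrasts**

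Two-arm simulation: 28 per arm, ρ = 0.5, 20,000 runs, no true difference.

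| Shift, ketamine / placebo (SD) | Bias in one-week arm difference (SD, absolute) | Arm difference rejects | Group-by-time rejects |
|---|---|---|---|
| 0.3 / 0.3 | 0.00 | 5.0% | 5.1% |
| 0.3 / 0 | 0.30 | 19.5% | 19.8% |
| 0.5 / 0.2 | 0.30 | 19.9% | 19.8% |

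With a common shift the randomised contrasts keep their 5% level. Only a shift that differs by arm distorts them, and nothing in the documents shows that one would.

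**The case against.** The strongest reply is that the trial is randomised and both arms follow the same schedule, as General Approach says. A common shift cancels, a concurrent placebo arm would display any spurious improvement, and the 24-hour hypothesis is untouched. Section 9.3 also ties testing within groups to the 4-hour and 24-hour points, before the call. All of this stands, and it limits the point to how Hypothesis 2 is read. It does not remove it, because no section says that Hypothesis 2 is decided by the arm difference at one week.

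The phone call also has a purpose: Section 9.3 gives response rate as a reason for it. Replacing it with email or unsupervised return could lose patients and would turn one uniform mode into a mixture. That stands too, so the call should be kept.

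Four stronger readings might be inferred, and the documents do not support them:

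- *That email is a second mode for the BSSI.* Section 10.2 says "A separate authorization for the use of email in the one week follow up will also be requested at the time of consent", but not that the questionnaire is sent that way; the purpose could be contact or scheduling.
- *That the protocol contradicts its own reasoning.* The phrase "To avoid poor interrater reliability, rater bias, and variable interview quality" in Section 9.2 explains the choice of the MADRS-S over the clinician-rated scale. It is not about the BSSI.
- *That the evaluator rates the patient.* Administering can mean reading out the self-report items and marking the answers. The bibliography lists a publisher's page on giving the scale by telepractice, so remote use was foreseen, though the documents offer no evidence that phone and paper scores agree.
- *That an unblinded interviewer biases the arm comparison.* Sections 9.4 and 10.1 mask outcome assessors. Guessing the arm remains possible, but that is a question of blinding, not of mode.

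**Conclusion.** The point holds in a limited form. Within-patient change to one week is fully confounded with the switch from self-completed paper to an evaluator on the phone, and item 5 of the Experimental Procedure together with the longitudinal rows of Table 6 leaves that change available as the evidence for durability. It should be settled before data are collected, because mode and time cannot be separated afterwards.

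A reader might go further and conclude that the one-week treatment comparison is biased, or that the trial faces a false-positive risk of up to 91%. Neither follows. The arm difference is unbiased under a shift common to both arms, and the percentages belong to an unplanned paired test under assumed shifts, correlations and equal SDs. The true size of the mode effect is unknown. Paper at 4 h and 24 h is inferred; if it were wrong, the change from baseline to one week would still cross modes. The consequence is confined to a secondary aim.

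**What to change.** 1. In Section 11.6, state that Hypothesis 2 is tested by the ketamine-placebo difference in BSSI at one week, taken as the group contrast at that visit from whichever longitudinal model in Table 6 is fitted. State that within-arm change to one week is descriptive because the mode of administration changes there.
2. In Section 10.1, keep the single phone call for all patients. Specify that the masked evaluator takes down the patient's own answers to the self-report items verbatim and adds no interviewer rating. Where possible, give the patient a blank copy of the form beforehand. State the mode of the one-week MADRS-S as well.
3. Add one field to the data collection sheet for the mode actually used for each form, and add the mode change to the limitations in Section 10.1.

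The cost is a few sentences, some printed forms and one data field. The small downside is that some patients will not have the form to hand; for them the items are read out and this is recorded.
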